8.2. Study Population and Setting

The analysis population will be identified from the OPERA Observational Database according to the inclusion criteria defined below.

Primary population

1) A diagnosis of HIV-1, a positive HIV-1 Western Blot, or a positive HIV-1specific ELISA; and a detectable HIV-1 viral load test

- 2) At least 18 years of age at the index date
- 3) Male or female patients
- 4) Prescribed DTG, RPV, RAL, BIC, EVG/c and DRV(/r/c) as part of a 3-drug regimen for the first time between 01AUG2013 and 31DEC2017
- 5) Not exposed to >1 core agent of interest concurrently

Subjects with the following criteria will be excluded from the study sample:

- 1) HIV-negative
- A diagnosis of HIV-2, a positive HIV-1/HIV-2 Multispot, a positive HIV-2specific ELISA, a positive HIV-2 Western Blot or a detectable HIV-2 viral load test
- 3) Women who are considered pregnant at the index date
- 4) Transgender patients (potential for weight changes due to hormone use)

Secondary population

The study population for the secondary objectives will be a subset of the primary study population meeting the following additional inclusion criteria:

- Patients switching to DTG, RPV, RAL, BIC, EVG/c or DRV(/r/c) as part of a 3-drug regimen for the first time between 01AUG2013 and 31DEC2017 (excluding ARTnaïve patients)
- Patients with a viral load <200 copies/mL at last viral load test prior to switch to core agent of interest

The descriptive primary objective (1) will be stratified by prior ART exposure (ART-naïve and ART-experienced. The primary objective assessing association between core agent and BMI change (2), and the secondary objective will be restricted to ART-experienced patients. ART-experienced will be defined as history of ART prior to initiation of the core agent of interest, or a baseline viral load of <1000 copies/mL.

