8.3.3. Study covariates

The following patient demographic and clinical characteristics will be assessed when first entering the healthcare setting at one of the designated clinics or within the 12-month baseline period preceding the index date. Data from the visit closest to the index date will be used for analysis.

Demographic variables

- Age
 - Continuous (years)
 - Categorical:
 - i. 18-25 years old
 - ii. 26-49 years old
 - iii. 50+ years old
- Gender
- Race/ethnicity (Black non-Hispanic, Black Hispanic, non-Black Hispanic, American Indian, Native Hawaiian, Pacific Islander, Asian, White non-Hispanic)
- History of injection drug use (yes/no)
- Marital status (e.g., single, married/domestic partnership, widowed, divorced/separated, unknown)
- Geographic region (i.e., Northeast, Midwest, South, West)
- Payer type (i.e. Medicaid, Medicare, commercial insurance, AIDS drug assistance programs (ADAP)/Ryan White, cash, no payer information available)

Virologic variables

- HIV viral load at baseline
 - Continuous (copies/mL and log₁₀ copies/mL)
 - Categorical (naïve):
 - Low (<10,000 copies/mL)
 - Moderate (≥10,000 to <100,000 copies/mL)
 - High (≥100,000 copies/mL)
 - Missing
 - Categorical (experienced):
 - Undetectable (<50 copies/mL)
 - Suppressed (≥50 to <200 copies/mL)
 - Viremic (≥200 copies/mL)
 - Missing

Immunologic variables

- CD4 cell count at baseline
 - Continuous (cells/μL)
 - Categorical:
 - High (CD4 > 500 cells/μL)
 - Moderately High (CD4 count >350 to ≤500 cells/µL)
 - Moderate (CD4 count >200 to ≤350 cells/µL)
 - Moderately Low (CD4 count >50 to ≤200 cells/µL)
 - Low (CD4 count ≤50 cells/µL)
 - Missing

Clinical variables

- Year of ART initiation
- Length of previous regimen (ART-experienced patients only)
- Time between index and end of follow-up (months)
- AIDS defining illnesses at baseline
- Mortality Risk (VACS Mortality Index)
- Comorbid conditions occurring on or before the index date (including T2DM and thyroid disease)
- HCV and HBV co-infection
- Blood pressure
- Concomitant medications associated with weight gain [31, 32] (these medications will be characterized and considered for inclusion in the statistical adjustment set)
 - Definite:
 - i. Antipsychotics and mood stabilizers
 - chlorpromazine, clozapine, haloperidol, lithium, olanzapine, valproic acid, risperidone, quetiapine
 - ii. Antidepressants
 - phenelzine, tranylcypromine, citalopram, amitriptyline, nortriptyline, mirtazapine, paroxetine

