 - iii. Antihyperglycemics
 - 1. insulin, chlorpropamide, gliclazide, glyburide, pioglitazone, rosiglitazone, repaglinide, tolbutamide, rosiglitazone
 - iv. Antihypertensives
 - 1. atenolol, metroprolol
 - v. Corticosteroids

- 1. cortisone, prednisolone, prednisone, methylprednisolone, hydrocortisone
- vi. Hormones
 - 1. human growth hormone/somatropin
 - 2. medroxyprogesterone
- vii. Anticonvulsants
 - 1. Gabapentin, valproic acid/sodium valproate, carbamazepine
- viii. Antihistamines
 - 1. cyproheptadine
- Concomitant medications associated with weight loss (these medications will be characterized and considered for inclusion in the statistical adjustment set)
 - Definite:
 - i. Anti-infectives
 - 1. metronidazole, amphotericin, atovaquone, pyrimethamine, ethionamide
 - ii. Antineoplastics
 - aldesleukin and interleukin-2, capecitabine, carboplatin, cytarabine, dacarbazine, fluorouracil, hydroxyurea, imatinib, irinotecan, methotrexate, vinblastine sulphate, vinorelbine tartrate
 - iii. Bronchodilators
 - 1. salbutamol sulphate, theophylline
 - iv. Cardiovascular drugs
 - 1. amiodarone, acetazolamide, hydralazine HCl, quinidine
 - v. Stimulants
 - 1. methylphenidate HCl, phentermine
 - vi. Antidepressants
 - 1. fluoxetine, bupropion
 - vii. Anticonvulsants
 - 1. topiramate
 - viii. Antihyperglycemics
 - 1. exenatide, liraglutide, semaglutide
 - ix. Anti-inflammatories
 - 1. sulphasalazine
 - x. Weight loss drugs
 - 1. bupropion-naltrexone, liraglutide, lorcaserin, orlistat, phentermine-topiramate
 - xi. Dementia treatment
 - 1. galantamine, rivastigmine

• Number of classes of ART experience prior to baseline (ART-experienced patients only)

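### Hormone use is the stated reason for excluding all transgender patients, yet for everyone else androgens, anabolic steroids and oestrogens are neither excluded nor on the list of weight-affecting drugs used for adjustment

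*Protocol*

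**What the plan says.** **Exclusions (Protocol 8.2).** Four groups are excluded. Two exclusions concern HIV status. The third is "Women who are considered pregnant at the index date". The fourth is "Transgender patients (potential for weight changes due to hormone use"). It applies to every transgender patient, whether or not that patient takes hormones. No exclusion names a drug.

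**Covariates (Protocol 8.3.3).** Drugs linked to weight gain and to weight loss are itemised by class under a heading that marks them as definite. The class for hormones in the weight-gain list has two entries, "human growth hormone/somatropin" and "medroxyprogesterone". Elsewhere the same list has corticosteroids, "cyproheptadine" among the antihistamines, and mirtazapine among the antidepressants ("phenelzine, tranylcypromine, citalopram, amitriptyline, nortriptyline, mirtazapine, paroxetine"). The weight-loss list includes a class defined by purpose: "bupropion-naltrexone, liraglutide, lorcaserin, orlistat, phentermine-topiramate". The weight-gain list has no class of that kind. Of both lists the section says that "these medications will be characterized and considered for inclusion in the statistical adjustment set".

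**Model (Protocol 8.5.1).** Drugs associated with weight gain and loss are among the covariates fixed in advance from the literature. Other factors may enter if the descriptive analyses show them to be related to both exposure and outcome. The baseline description covers the covariates of 8.3.2 and 8.3.3. The model is stratified by baseline BMI category.

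**The concern.** The protocol's own reasoning is that hormone use can move weight enough to justify removing a whole group. The same reasoning applies to a non-transgender patient who takes testosterone, an oestrogen or an anabolic steroid, but that patient enters the cohort and the drug is not recorded as a covariate. In a source database with 14.8% women among HIV-positive patients (8.4), the only sex hormone listed is a progestin, and no androgen appears.

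If such drugs change BMI and are used more often with one core agent than another, part of their effect is credited to the core agent. The study is meant to inform a weight-gain signal for DTG (6.2), and the agent differences quoted in 6.1 are a few tenths of a kg/m² or less. A small unmeasured co-treatment effect could therefore matter.

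**Working it through.** **Step 1: can an unlisted drug reach the model?**

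- By exclusion: no, since 8.2 has no drug criterion.
- By the a priori set: no, if the weight-affecting drugs of 8.5.1 are those itemised in 8.3.3. Those lists are itemised and carry no open-ended entry.
- By the descriptive route in 8.5.1: no, because a drug absent from 8.3.2 and 8.3.3 is not described.

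Followed as written, the plan leaves androgens, anabolic steroids, oestrogens and any unlisted drug given to raise weight unadjusted. The listed items (somatropin, medroxyprogesterone, cyproheptadine, mirtazapine, corticosteroids) are not affected.

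**Step 2: the quoted agent differences.** Section 6.1 reports mean 12-month BMI increases in ART-experienced patients of 0.30 (DTG), 0.24 (RAL), 0.23 (EVG), 0.41 (DRV) and 0.06 (RPV).

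- DTG − RAL = 0.30 − 0.24 = 0.06
- DTG − EVG = 0.30 − 0.23 = 0.07
- DTG − DRV = 0.30 − 0.41 = −0.11
- DTG − RPV = 0.30 − 0.06 = 0.24

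In absolute size they run from 0.06 to 0.24 kg/m².

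**Step 3: possible bias.** For an omitted yes/no covariate in a linear model, bias = γ × Δp. Here γ is the extra BMI change in users and Δp is the difference in use between two core-agent groups that remains after the other adjustments. The protocol gives neither, so both are assumptions.

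| γ (kg/m²) | Δp = 1 point | 2 points | 5 points | 10 points |
|---|---|---|---|---|
| 0.5 | 0.005 | 0.010 | 0.025 | 0.050 |
| 1.0 | 0.010 | 0.020 | 0.050 | 0.100 |
| 1.5 | 0.015 | 0.030 | 0.075 | 0.150 |

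To equal the smallest quoted difference, Δp must be 0.06/0.5 = 12 points, 0.06/1.0 = 6 points or 0.06/1.5 = 4 points. To equal the largest at γ = 1.5, it must be 0.24/1.5 = 16 points.

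**Step 4: is Table 2 a usable yardstick?** All ten sample sizes in Table 2 (8.5.3) reproduce exactly, from 29,832 at ρ = 0.02 to 292 at ρ = 0.20. The calculation is a noncentral F test with 4 tested degrees of freedom, 14 predictors, λ = nρ²/(1 − ρ²), 80% power and alpha 0.05 (alpha is not stated and is assumed). The conversion d = 2ρ/√(1 − ρ²) reproduces the tabulated differences.

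The row for 0.08 needs 7,453 patients, more than the largest BMI stratum (6,598). At the stratum sizes given, the same method yields detectable differences of about 0.085 (normal weight, 6,598), 0.087 (overweight, 6,298), 0.11 (obese, 3,964) and 0.31 (underweight, 510). The conversion contains no standard deviation, so these are in kg/m² only if that standard deviation is 1. The differences in Step 2 are the better comparison.

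**The case against.** **The lists already cover much of this, and final code lists often belong elsewhere.** A reader might infer that hormone and anabolic use outside the transgender group is wholly uncaptured. The documents do not support that: two hormones, an appetite-raising antihistamine and mirtazapine are listed, and 8.5.1 adjusts for listed drugs. It is also true that drug codes are commonly settled in a later specification. But here the protocol fixes the classes itself, and the missing ones belong to the very category it uses to justify an exclusion.

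**Confounding is not shown.** This stands. Nothing in the protocol says that use of these drugs differs by core agent, or that wasting drives both their use and the choice of agent. Stratification by baseline BMI and adjustment for comorbid conditions and for change in viral load and CD4 count would absorb part of any common cause. AIDS-defining illness and the mortality index are recorded and could be added. Only the remaining imbalance counts. The outcome is change from baseline, so long-term users whose weight has settled would add little.

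**The underweight stratum.** A reader might infer that the damage is greatest there, because drugs for low weight are most likely there. That is plausible, but the protocol has no data on it. Even the largest assumed bias, 0.15, is about half of the 0.31 that 510 patients can detect on the protocol's own method.

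**Unequal handling is not a contradiction.** Excluding a group in which hormone use is expected, while adjusting for drugs in others, is a legitimate design choice. That is accepted. The gap is that the adjustment side is incomplete.

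**Conclusion.** The gap holds on the text. The protocol names hormone use as a cause of weight change, excludes one group for it, and gives no means of handling most hormones in everyone else. The consequence is possible confounding, with size and direction unknown. Under the assumed ranges the bias is 0.005 to 0.15 kg/m². At differences in use of 1 to 2 points it is 0.005 to 0.03, below every quoted agent difference. It reaches the smallest of them (0.06) only with a residual difference in use of 4 to 12 points, depending on the effect.

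It would go too far to conclude that the DTG comparisons are biased, or that weight-changing co-treatment in general is unadjusted. The first needs figures on use by agent that the protocol does not give, and the second overlooks the drugs that are listed. Severity: minor.

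**What to change.** 1. In 8.3.3, add to the weight-gain list androgens and anabolic steroids, oestrogens, and a class for drugs prescribed to raise weight, as the counterpart of the existing weight-loss class. Pool rare items into one indicator.
2. In 8.5.1, place that indicator in the a priori adjustment set. Reconcile the two sections: 8.3.3 says only that "these medications will be characterized and considered for inclusion in the statistical adjustment set", whereas 8.5.1 treats such drugs as chosen in advance.
3. Report use of the added drugs by core agent at baseline, so that the assumed differences above can be replaced by observed ones.
4. Add a sensitivity analysis that leaves out baseline users, which applies the reason given in 8.2 evenly.

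**Cost.** The drug list is longer and the model gains one covariate. The health records described in 8.4 already have to supply the other co-medications, so no new data collection should be needed. The indicator may be sparse, mainly in the 510-patient underweight stratum. Drugs started after the index date remain unaddressed.

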In the current ART era, weight gain has been attributed to the effect of the treatment rather than simply an improvement in health with increases in weight following initiation of ART reported in multiple studies [17, 18, 25, 26]. In the NA-ACCORD, 22% of patients with normal BMI at baseline became overweight and 18% of patients who were overweight at baseline became obese after just three years of ART [17]. Out of 1,255 HIV patients enrolled in the U.S. Military Natural History Study between 1985–2004 and followed up to 2007, 62% gained weight after HIV diagnosis, among whom BMI increased by 2.3 kg/m² on average from baseline to last visit (average rate of 0.55 kg/m²) per year). The average weight gain was 7.3 kg with an average rate of 1.71 kg per year [18]. Among 1,600 HIV patients initiating ART in the Swiss HIV Cohort Study, BMI increased on average by 0.92 kg/m² per year (95% CI: 0.83, 1.0) in the first year of ART and 0.31 kg/m² per year (0.29, 0.34) during years 1-4 [24]. Among 1,160 women in the Women's Interagency HIV Study (WIHS), median BMI increases over 5 years were 0.21 kg/m² (90% CI: –1.33, 0.42) for normal baseline BMI, 0.39 kg/m² (90% CI: 0.15, 0.66) for overweight, 0.31 kg/m² (90% CI: -1.18, 0.67) for obese, and -0.36 kg/m² (90% CI: -2.04, 1.08) for morbidly obese women [25]. In the Veterans Aging Cohort Study (VACS), 4,311 ART-naïve patients initiating ART between 2000-2008 gained a median of 2.7 kg (IQR: -1.3 to 7.7) [26].

In addition, duration of ART exposure may also impact weight gain. Between 1999 and 2004 in the Multicenter AIDS Cohort Study (1,059 men living with HIV) and the WIHS cohorts (1,455 women living with HIV), a shorter duration of ART was associated with lower BMI [19]. These studies suggest that both ART initiation in general and time since initiation are associated with increases in BMI and weight [17-19, 25, 26].

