6.2. Rationale

Disentangling weight gain due to improved health status from weight gain due to an undesired effect of therapy requires an assessment of a large number of patients who may be progressing toward a stable health status or in whom a stable health status has been achieved and maintained.

Following raised disproportionality analysis (DPA) scores for both DTG and DTG/ABC/3TC detected through the routine pharmacovigilance, clinical trial data, spontaneous case reports, and published studies were reviewed. The cumulative evidence could not rule out an association between DTG exposure and weight gain, leading to a recommendation for a label change indicating weight gain as an uncommon ADR. This analysis, utilizing data from a large real-world population of treated HIV patients, will provide additional information to support the signal evaluation.

7. **RESEARCH QUESTION AND OBJECTIVE(S)**

Primary:

- Among new users of DTG, RPV, RAL, BIC*, EVG/c and DRV(/r/c): To describe BMI categories, weight, lipid levels (e.g. total cholesterol, HDL, LDL, triglycerides), and lipodystrophy at core agent initiation and at 6,12, and 24 months after core agent initiation, stratified by ART- naïve and ARTexperienced.
- Among ART-experienced new users of DTG vs. RPV, RAL, BIC*, EVG/c or DRV (/r/c): To estimate the association between specific core agent initiation and changes in BMI at 6, 12, and 24 months after core agent initiation.

Secondary:

 Among ART-experienced patients who were suppressed at switch (stable switch) to DTG, RPV, RAL, BIC*, EVG/c, or DRV(/r/c): To describe BMI categories, weight, and lipid panels levels (e.g. total cholesterol, HDL, LDL) at core agent initiation, and at 6,12, and 24 months after core agent initiation

*Due to recent approval and more limited potential follow-up, patients taking BIC will be included for 6-month outcomes only.

8. **RESEARCH METHODS**

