8.5.2. Analysis of secondary objectives

These analyses will be conducted only among ART-experienced new users of RPV, RAL, EVG/c, BIC, DRV(/r/c), or DTG who were virologically suppressed at the time of switch to a core agent of interest (stable switch). Using data from the most recent visit in the 12-month baseline period preceding the index date of core initiation, patients with a HIV-1 RNA viral load measurement < 200 copies/mL will be considered suppressed.

Baseline demographic and clinical characteristics

All baseline outcomes and covariates listed in sections 8.3.2. and 8.3.3. will be summarized for patients who have achieved virologic suppression (<200 copies/mL) prior to switch to RPV, RAL, EVG/c, DRV(/r/c), BIC, or DTG between 01AUG2013 and 31DEC2017; medians and interquartile ranges for continuous variables and counts and percentages for categorical variables will be provided.

Description of follow-up levels of total cholesterol, HDL, LDL, triglycerides, weight and BMI

Total cholesterol, HDL, LDL, triglycerides, weight, and BMI will be assessed continuously at 6,12, and 24 months after initiation. BMI and lipids will also be assessed categorically, as the proportion of patients in each BMI and lipid category and the proportion of patients changing categories of BMI among patients initiating each core agent of interest (see section 8.3.2 for a definition of changes in categories).

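### The comparative BMI model runs only in the pooled ART-experienced group and the stable-switch subset is only described, so return-to-health gain is incompletely separated from drug effect

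*Protocol*

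**What the plan says.** All references are to the protocol.

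- **Aim.** Section 6.2 presents the task as "Disentangling weight gain due to improved health status from weight gain due to an undesired effect of therapy". It says this needs many patients who are either moving toward stable health or already there, and it describes the study as added information for evaluating the DTG weight signal.
- **Population of the comparative model.** Section 8.2: "The primary objective assessing association between core agent and BMI change (2), and the secondary objective will be restricted to ART-experienced patients". It adds: "ART-experienced will be defined as history of ART prior to initiation of the core agent of interest, or a baseline viral load of <1000 copies/mL". No minimum time on ART, interruption rule or suppression rule is given.
- **Viremic patients.** Section 8.3.3 gives experienced patients a baseline viral load level of "Viremic (≥200 copies/mL".
- **The model.** Section 8.5.1 fits adjusted linear regressions of BMI change at 6, 12 and 24 months, stratified by baseline BMI category only. The named adjusters are age, sex, race/ethnicity, comorbid conditions, weight-related medications, and change in viral load and CD4 count. Other factors found in the descriptive work may be considered.
- **Stable switch.** Section 8.2 defines the subset by a last viral load below 200 copies/mL before the switch. Section 7 sets its objective as description. Section 8.5.2 plans: "Total cholesterol, HDL, LDL, triglycerides, weight, and BMI will be assessed continuously at 6,12, and 24 months after initiation". Unlike section 8.5.1, it plans neither pairwise tests nor a model.
- **Background.** Section 6.1: "These studies suggest that both ART initiation in general and time since initiation are associated with increases in BMI and weight".

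**The concern.** Patients who are viremic, restarting after a gap, or early in their first ART can gain weight because their health is recovering, whichever agent they take. If DTG and a comparator are started in different mixes of such patients, part of the BMI contrast reflects the stage of recovery. Among patients already suppressed at the switch this source of gain should be smaller, and that subset is already defined. It yields no comparison between agents.

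What is at stake is how far the DTG-versus-comparator estimates can inform the signal evaluation. The contrasts cited for ART-experienced patients are a few tenths of a BMI unit or less, so a modest imbalance matters.

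**Working it through.** **1. Who can enter the pooled model.** Viremic patients are explicit in section 8.3.3. Restarting and recently started patients are an inference: nothing in section 8.2 excludes them. Section 8.3.1 narrows the recently started group, because prior use of another core agent of interest after entry into the database is not allowed. Patients who recently started a different core agent, or whose ART began before database entry, can still qualify.

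**2. What the planned adjustment covers.** The sentence in section 8.5.1 announces baseline variables but lists changes in viral load and CD4 count, which on the natural reading need a value after initiation. Section 6.1 reports faster viral load decline and larger CD4 gains with INSTIs than with PIs or EFV. On the protocol's own account these changes may be affected by the agent, most directly for DTG versus DRV, and adjusting for them may remove part of an agent effect. They also miss the patient who started ART recently and is already suppressed, since little viral load change remains.

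**3. Unadjusted size, for illustration.** Section 6.1 cites BMI gains of 0.92 kg/m² per year in the first ART year and 0.31 in years 1 to 4 (Swiss cohort of ART initiators).

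- Gap: 0.92 − 0.31 = 0.61 kg/m² per year.
- Shift in a 12-month contrast = gap × difference in share of early or restarting patients.
- 10 points: 0.61 × 0.10 = 0.06. 20 points: 0.61 × 0.20 = 0.12.
- Wider range, with an extra gain of 0.3 to 0.74 and a difference of 5 to 20 points: 0.3 × 0.05 = 0.015 up to 0.74 × 0.20 = 0.148.

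Cited 12-month means in ART-experienced patients are DTG 0.30, RAL 0.24 and RPV 0.06. The contrasts are 0.30 − 0.24 = 0.06 and 0.30 − 0.06 = 0.24.

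**4. How much the planned adjustment may remove.** A simulation with no drug effect assumed a viremic share of 35% versus 20%, an extra gain of 0.74 in viremic patients, an SD of BMI change of 1.5, and 100%, 80% or 60% of viremic patients becoming suppressed.

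| Analysis | Spurious contrast, kg/m² |
|---|---|
| Unadjusted | 0.064 to 0.123 |
| Adjusted for change in viral load | 0.004 to 0.064 |
| Suppressed patients only | −0.010 to 0.015 |

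The unadjusted values agree with 0.74 × 0.15 = 0.111, or 0.111 × 0.6 = 0.067 when only 60% suppress and gain follows suppression. Differences of about 0.015 are simulation noise. The residual is largest when many viremic patients stay viremic but still gain. The 0.74 is 0.92 − 0.18 and mixes a yearly rate with a 6-month mean. Scaled to 0.61, the largest residual is 0.064 × 0.61/0.74 = 0.053. The simulation leaves out adjustment for CD4 change, any agent effect on viral load, and recently started suppressed patients.

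**5. Whether the subset is large enough.** Table 2 in section 8.5.3 was reproduced first: an F test with 4 and n − 15 degrees of freedom (4 exposure terms, 10 covariates), noncentrality n × ρ²/(1 − ρ²), and alpha 0.05 assumed because none is stated. All ten sample sizes match, for example 1187 at ρ = 0.10 and 292 at ρ = 0.20. The protocol's formula inverts to d = 2ρ/√(1 − ρ²). The suppressed share is not given, so 30% to 90% is assumed.

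| Group (n) | Full group | 90% | 50% | 30% |
|---|---|---|---|---|
| All (17,370) | 0.052 | 0.055 | 0.074 | 0.096 |
| Normal weight (6,598) | 0.085 | 0.090 | 0.120 | 0.156 |
| Overweight (6,298) | 0.087 | 0.092 | 0.123 | 0.159 |
| Obese (3,964) | 0.110 | 0.116 | 0.155 | 0.201 |
| Underweight (510) | 0.307 | 0.324 | 0.437 | 0.568 |

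Entries are detectable d at 80% power. On this formula d is a standardised difference and equals BMI units only if the SD is 1; at an SD of 1.5, 0.074 becomes 0.074 × 1.5 = 0.111 kg/m².

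**The case against.** The strongest reply is that the protocol already controls for recovery. Change in viral load and CD4 count are direct markers of it, and in the simulation viral load change alone removed much of the bias. The adjustment list is open, section 8.3.3 collects baseline viral load, baseline CD4 count, year of ART initiation and length of previous regimen, and section 8.5.1 tests every baseline covariate between DTG and each comparator. The rationale deliberately wants patients both moving toward and already in stable health. Final covariate sets and subset analyses may also sit in an analysis plan that is not at hand.

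Much of this stands. A reader might infer that drug effect cannot be separated from recovery at all, or that the study fails its purpose. The documents do not support that, given the planned adjustment and the modest stated purpose. A reader might also infer that imbalance could explain the whole DTG minus RPV contrast. That would need a 40-point difference in shares (0.61 × 0.40 = 0.24) with no adjustment at all, and nothing in the protocol suggests such a figure.

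What the reply leaves open is narrower. Further confounders are only to be considered, and the changes arise after initiation. The limit to description is set by the objectives in section 7, so it is a choice made in the protocol itself. If both kinds of patient are wanted, that argues for showing the agent comparison in the stable group too.

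**Conclusion.** The point holds in a limited form. The only DTG-versus-comparator BMI-change model pools viremic and suppressed experienced patients, and the subset better suited to the stated aim gets no comparison. Return-to-health gain is therefore incompletely separated from drug effect.

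The illustrative unadjusted shift is about 0.06 to 0.12 kg/m² at 12 months. It assumes a 10 to 20 point difference in shares and applies a gap seen in ART initiators in full to experienced patients. After adjustment for viral load change, the simulated residual runs from near zero to about 0.06, at most about the size of the cited DTG minus RAL contrast. The true shares are unknown, so none of these figures estimates the bias in the planned model.

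A reader might infer that the stable-switch subset should become the sole basis for any drug-effect conclusion. The documents do not support that either: it would replace the sponsor's primary objective, and a single viral load below 200 copies/mL does not show sustained stability.

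**What to change.** 1. In section 8.5.2, add the adjusted DTG-versus-comparator BMI-change model from section 8.5.1, fitted in the stable-switch subset. Pre-specify it as a supporting analysis reported beside the all-experienced primary model, and extend the secondary objective in section 7 to match.
2. In section 8.5.1, place baseline viral load category, baseline CD4 count and time on ART in the a priori adjustment set. Time on ART can be built from year of ART initiation and length of previous regimen, with a missing category. Control for stage of recovery then no longer rests on the post-initiation changes alone.
3. Use the time-on-ART covariate in the subset model too, because recently started patients who have just become suppressed can enter it.

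The cost is protocol wording and one more run of an existing model on a defined subset. Intervals will be wider there, chiefly in the underweight stratum. Year of ART initiation is coarse, so some difference in time on ART will remain.
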